- Defense and Veteran's Pain Rating Scale (DVPRS) basic will capture pain daily.
- Single Assessment Numeric Evaluation (SANE) will capture function daily.
- Activity and medication use will also be recorded in a self-report diary.

- Knee Injury and Osteoarthritis Outcome Score (KOOS) will capture knee symptoms and associated functional status at baseline, 3 weeks, and 6 weeks post-intervention.
- The Veterans Rand 12 Item Health Survey (VR-12) will capture overall functional and health status at baseline, 3 weeks, and 6 weeks post-intervention.

PRP CBC analysis results will be reported on Appendix G (CBC Results CRF).

A chart review will be conducted at the end of 6 weeks to capture all SOC/PT visits.

We will use protein expression quantification and genetic analysis to target specific biomarkers in the areas of inflammatory mediators, growth factors, and intra-articular, structural homeostasis mediators.

10.3 At any point in the study, will you request, use, or access health information in any form, including verbal, hard copy and electronic?

- Yes No

10.4 Review the definitions below and respond to the following two questions. If you are not sure of the answers, email [contact] for assistance. The *Military Health System (MHS)* is defined as all DoD health plans and DoD health care providers that are organized under the management authority of, or in the case of covered individual providers, assigned to or employed by, the Defense Health Agency (DHA), the Army, the Navy, or the Air Force. *MHS workforce members* are employees, volunteers, trainees, and other persons whose conduct, in the performance of work for the MHS, is under the direct control of the MHS, whether or not they are paid by the MHS. *MHS business associates* are persons or entities that provide a service to the MHS and require protected health information (PHI) to provide the service.

Are you an MHS workforce member?

- Yes, I am an MHS workforce member
 No, I am not an MHS workforce member

Are you an MHS business associate?

- Yes, I am an MHS business associate
 No, I am not an MHS business associate

10.5 Have you consulted with an MHS data expert to determine the data elements required for your study?

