For categorical variables, statistical methods may include tests such as the Fisher's exact test, Chi-square test, McNemar's test, or binomial test. For ordinal variables that do not approximate a continuous variable, tests such as ordinal logistic regression will be performed. For ranked data, tests such as Friedman's test will be used. For continuous random variables (ratio or interval types) or ordinal data that approximates a continuous random variable (e.g., Likert scale), t-tests will be used. The Wilcoxon signed rank test or Wilcoxon rank sum test will be used if the assumptions for the t-test do not hold. The normality assumption may be evaluated with a test that is appropriate given the sample size, objective, and intended audience, e.g., Shapiro-Wilk test, Jarque-Bera test, Kolmogorov-Smirnov test, or Anderson-Darling test. For analyses with more than two groups in the single independent variable or for analyses with more than one independent variable, single or multi-way ANOVAs will be performed, respectively. If a continuous variable is a potential covariate, then an ANCOVA will be performed. Post hoc tests will include tests such as Tukey's, Dunn's, Dunnett's, or pairwise univariate tests with false discovery rate correction, depending on the objectives of the analysis. Sequencing data will be analyzed using techniques that include negative binomial regression, PERMANOVA, and ANOSIM. Clustering will be performed using techniques such as hierarchical, k-means, k-medoids, Gaussian mixture models. These methods will attempt to minimize (or maximize depending on the metric) an error metric such as silhouette score, Akaike Information Criterion, or Bayesian Information Criterion with the specific metric being selected based on the best practice in the field, e.g., silhouette score for k-means. Clustering may be performed with or without first performing dimensionality reduction using Principal Components Analysis, Non-metric Multi-Dimensional Scaling, t-SNE, U-MAP, or another similar technique, depending on the data types, number of variables, and objectives. When analytic methods are unavailable, bootstrapping may be performed to estimate uncertainties, e.g. confidence intervals. Alternatively, if Bayesian methods are applied, then credible intervals will be calculated. When decision trees and decision-tree based methods (e.g., random forest, decision jungles) are used, feature importance may be calculated. When developing predictive models, both simple, explainable models (e.g., linear and logistic regressions) will be used when possible. When incorporating larger numbers of variables, neural network based models may be used. When such methods are applied, the optimum number of layers, dropout, activation functions, nodes, and other elements of model architecture will be determined empirically. Data will be split into training, cross validation, and testing groups in accordance with best practices in the machine learning and artificial intelligence fields. Regarding correlation analyses, correlations will be identified via methods that include Pearson's, Spearman's, and Kendall's tau. The specific method will be selected based on the bivariate distribution of the data, e.g. monotonic and linear vs. monotonic but not linear. Hoefding's D statistic may be calculated for non-monotonic relationships.

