11.5 Please provide a justification for your sample size

Since this is a discovery-based study of a novel topic, limited data are available with which to perform a power analysis. Thus we used a G*Power for a general comparison analysis without needing to root firmly in one specific variable.

If we are able to enroll 150 participants (a minimum of 92 post-attrition), assuming an effect size of .2, we will achieve 90% power. Effect size assumptions were taken from Tomazoni et al. 2016 based on the comparison of control versus PBMT with regards to biomarkers of gene expression that we assume to be an acceptable proxy for our primary comparison with regards to our biomarkers of concern. Significance threshold for power calculations was considered to be .01 to account for false discovery rate within our set of primary biomarker outcomes. Power calculations were performed using the WebPower package and the R Programming language.

11.6 Data Analysis Plan: Complete description: Background, Objectives, Design, Step by Step how the project is going to be done, Data analysis plan:

Aim 1 will be evaluated by comparing the PRP only and the PRP + PBMT treatment arms at six weeks relative to baseline. Generalized additive models predicting the fractional change in outcome measure at 6 weeks will be used.

Aim 2 will compare across all four treatment arms and will use Multi-Level models comparing the three treatment arms across time points and including random effects.

Aim 1 will include biomarker measures only; Secondary Aim 2 will include both biomarker measures and self-reports.

Hypothesis tests will be two-tailed and statistical significance will be considered at the putative threshold ($\alpha=0.05$). Any secondary P-values will be subject to a false discovery rate adjustment in keeping with best statistical practices. Multilevel models will incorporate random effects to account for repeated measures, using distribution families and link functions appropriate for the outcomes of interest, determined using QQ plots analyzed for best model fit. All statistical analyses will be performed using the R Programming language.

Clinical outcomes (pain scores) will be evaluated via ANOVA and post-hoc tests (Tukey's HSD test). A non-parametric alternative will be used if assumptions are not met.

Molecular Analyses:

DNA/RNA Analyses

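### Self-reported pain falls under both the Aim 2 multilevel model and an ANOVA with Tukey tests, and section 11.6 does not say which one decides

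*Combined protocol and SAP*

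**What the plan says.** Two statements in section 11.6 (Data Analysis Plan) bear on pain.

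- By outcome type: "Aim 1 will include biomarker measures only; Secondary Aim 2 will include both biomarker measures and self-reports". Aim 2 "will use Multi-Level models comparing the three treatment arms across time points and including random effects", and "Multilevel models will incorporate random effects to account for repeated measures". Secondary P-values receive a false discovery rate (FDR) adjustment.
- By name, a little later: "Clinical outcomes (pain scores) will be evaluated via ANOVA and post-hoc tests". The post-hoc test is Tukey's HSD, with an unnamed non-parametric alternative if assumptions fail.

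On data collection, section 10.2 says of the pain scale: "DVPRS) basic will capture pain daily". Section 10.1 has participants keep that log for 6 weeks. Section 10.2 schedules KOOS and VR-12 at baseline, 3 and 6 weeks. It describes DVPRS (pain) and SANE (function) only as daily.

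Section 9.3 makes self-reported pain and function by treatment the subject of Aim 3. Section 11.6 never mentions Aim 3.

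The general rules in section 11.1 say that, with more than two groups or more than one independent variable, "single or multi-way ANOVAs will be performed, respectively". They add: "If a continuous variable is a potential covariate, then an ANCOVA will be performed".

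**The concern.** A pre-specified plan should lead two statisticians with the same data to the same pain result. Here one could fit the multilevel model and the other an ANOVA with Tukey tests, and each could cite section 11.6. Nothing makes one of them primary or calls the other a sensitivity analysis. The answer to a stated aim could then be chosen after both results are known. The ANOVA route leaves further choices open: which instrument, which day or summary of days, raw score or change, and whether baseline enters.

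**Working it through.** **Plan's own figure.** There is none for pain. The 90% power in section 11.5 concerns biomarkers, and this point does not depend on it.

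**The two routes side by side**

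| Feature | Aim 2 multilevel model | ANOVA with Tukey |
|---|---|---|
| Outcomes covered | Self-reports | Clinical outcomes, with pain scores given in brackets |
| Repeated scores | Across time points, random effects | Not stated |
| Baseline | Not stated as a covariate | Not stated; section 11.1 allows ANCOVA |
| Multiplicity | FDR for secondary P-values | Tukey's HSD |
| Incomplete participants | Section 11.1 keeps those missing baseline or week 6 | Section 11.1 default: drop observations with a missing value |

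The last row matters because section 11.5 foresees 150 enrolled falling to 92, a loss of (150 − 92)/150 = 38.7%.

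**Can the results differ?** The documents give no correlation or variance for pain, so these inputs are assumptions: four arms, one arm shifted by 0.6 SD, equal correlation ρ of 0.3, 0.5 or 0.7 between any two scores of a participant, two-sided 0.05, and 2,000 simulated trials per setting. Arm sizes are 92/4 = 23, and 31, because section 11.2 states 30 to 31 per arm (92/3 = 30.7). The comparison is a one-way ANOVA on one week-6 score against the same score adjusted for baseline. The second is a simple stand-in for a model that uses more than one score per person. It is not the multilevel model itself.

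| Per arm | ρ | Power, one-score ANOVA | Power, baseline-adjusted | Disagree on significance |
|---|---|---|---|---|
| 23 | 0.3 | 0.50 | 0.54 | 11% |
| 23 | 0.5 | 0.52 | 0.64 | 20% |
| 23 | 0.7 | 0.52 | 0.82 | 35% |
| 31 | 0.3 | 0.64 | 0.68 | 11% |
| 31 | 0.5 | 0.66 | 0.78 | 18% |
| 31 | 0.7 | 0.65 | 0.94 | 30% |

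**Where the efficiency comes from.** Variance is relative to a single post-treatment score, for ρ = 0.3, 0.5, 0.7.

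- Baseline adjustment, 1 − ρ²: 0.91, 0.75, 0.51.
- Mean of 42 daily scores, (1 + 41ρ)/42: 13.3/42 = 0.32, 21.5/42 = 0.51, 29.7/42 = 0.71.

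**Validity.** With no true difference, the one-score ANOVA rejects in 4.3 to 5.3% of trials, so it holds its level.

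**Choosing between the two.** With no true difference, the chance that at least one test is significant is (p1 + p2 + disagreement)/2. At 23 per arm this is:

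- ρ = 0.3: (0.047 + 0.049 + 0.029)/2 = 0.063
- ρ = 0.7: (0.049 + 0.052 + 0.075)/2 = 0.088

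Taking the better of the two would therefore lift a nominal 5% to roughly 6 to 9%.

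**The case against.** The overlap is not literally stated. Sections 10.1 and 10.2 keep the daily pain log apart from the questionnaire battery, so the Aim 2 self-reports could mean only KOOS and VR-12, with pain left to its own sentence. This carries some weight, but section 9.3 itself calls the outcome self-reported pain, so the overlap is close to certain. If the narrower reading was meant, the plan needs to say so.

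It is also fair that the study calls itself discovery-based, that section 11.6 labels Aim 2 secondary, and that no sample-size figure depends on pain. That limits the importance of the point but does not remove the conflict.

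Two stronger readings are tempting, and the documents do not support them.

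- A reader might infer that the plan commits to a one-way ANOVA that ignores baseline and the repeated scores. The pain sentence says neither. Section 11.1 makes one-way the natural default for a single factor, but it also provides for multi-way ANOVA and ANCOVA. The sentence is unspecified on these points.
- A reader might infer invalid standard errors. If all 42 daily rows were pooled as independent, the design effect 1 + 41ρ would be 13.3 to 29.7, and the simulated false-positive rate about 89 to 97%. The plan does not propose such an analysis, and the same section provides random effects for repeated measures.

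**Conclusion.** The point holds as an unresolved conflict. Pain is covered by two analyses with different multiplicity rules and different handling of incomplete participants. Neither is named as deciding, and the ANOVA is not specified well enough to be reproduced. On the stated assumptions, two reasonable versions disagree on significance in about 11 to 35% of trials at 23 per arm and 11 to 30% at 31 per arm. These percentages illustrate what the choice can do. They depend on the assumed correlations and effect, and on a baseline-adjusted stand-in for the multilevel model. In its ordinary form, with one score per person, the ANOVA costs efficiency and consistency but not validity. The plan should be changed, but the biomarker-only Aim 1 analysis is not affected.

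**What to change.** 1. Name the Aim 2 multilevel model as the single deciding analysis for pain, with DVPRS as the instrument. Use the repeated daily scores, for example as weekly means, with arm, time, arm × time and a participant random effect. State the deciding time point.
2. Delete the ANOVA and Tukey sentence, or label it a sensitivity analysis and give its outcome, time point and covariates.
3. Confirm whether a pre-treatment DVPRS and SANE score is recorded. Section 10.2 lists baseline only for KOOS and VR-12, and the baseline questionnaires in section 10.1 are not named. If one is recorded, adjust for it. If not, say so and fit the model without it; a log entry made after treatment starts is not a baseline.
4. State one multiplicity rule for the arm contrasts and reconcile it with the FDR rule in the same section.
5. While editing, tie the pain analysis to Aim 3, and correct the Aim 2 sentence, which refers to both four and three arms.

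The cost is small: SAP wording, and a check that a pre-treatment pain entry exists. The daily scores are already scheduled.

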DNA/RNA analyses will be performed using the software Galaxy or Geneious or any similar software packages such as Bioconductor for the R programming language. Specific statistical methods will depend on the variables of interest, but will include Fisher's exact test or Chi-square test for categorical data, logistic or linear regression for dependent variables with binary and continuous outcomes, respectively, and PCA, t-SNE, or U-MAP for dimensionality reduction, the first step in unsupervised clustering. The unsupervised clustering techniques that follow will include those listed above for microbiome profiling but may also include techniques better suited to specifically Cartesian coordinate data such as k-means. The latter would be accomplished following projection of the data into a Cartesian plane, e.g. via non-metric multidimensional scaling (NMDS). Data collected via the nCounter platform, qPCR data, or any data collected using a similar technology will be analyzed in accordance with the manufacturer's recommendations (e.g., t-test, linear regression, etc.). Sequence alignment for the purpose of biomarker identification (e.g., SNP detection) will be performed using Bowtie2 or similar software as standalone command line based software or via a graphic user interface (GUI) embedded within Galaxy, Geneious, or another package. Differential expression analysis for transcriptomic data will be performed using standard tools and workflows (e.g., Salmon, Kallisto, Sleuth, DESEQ2, edgeR, Coordinate Covariation Analysis, epigenomix, etc.).

Proteomic Analyses

Maximum-likelihood techniques based on the negative binomial distribution will be used to model proteomics count data and Wald statistics, two-tailed t-test, analysis will be utilized to analyze the primary and secondary outcomes. Any missing data that cannot be obtained via chart review or interview of the caring provider will be omitted and documented as such. In some case where the confounding variables cannot be eliminated or minimized through experimental design, the confounding variables will be included in the analysis to control for their effects. Data analysis will be conducted using both standalone proteome discoverer with Sequest, Mascot search engine and R-programming languages established for high throughput proteomics data analysis here in DCI. For orthogonal validation data sets will be analyzed with the various statistical algorithms that are established in DCI.

Correlation Analyses

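### The plan permits k-means on low-dimensional coordinates with silhouette choosing the number of clusters; that path always returns at least two groups, and no check that clusters exist is stated

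*Combined protocol and SAP*

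**What the plan says.** Clustering appears in two places in the combined protocol and SAP.

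- **Section 11.1, Statistical methods.** The algorithms are given by example: "Clustering will be performed using techniques such as hierarchical, k-means, k-medoids, Gaussian mixture models". The number of clusters is to be chosen by "an error metric such as silhouette score, Akaike Information Criterion, or Bayesian Information Criterion", matched to the method by field practice, and the one pairing given is "silhouette score for k-means". Prior reduction is optional: "Clustering may be performed with or without first performing dimensionality reduction using Principal Components Analysis", with NMDS, t-SNE and U-MAP among the alternatives.
- **Section 11.6, DNA/RNA Analyses.** Reduction is no longer described as optional: "PCA, t-SNE, or U-MAP for dimensionality reduction, the first step in unsupervised clustering". The only clustering technique named there is k-means, and it is tied to a projection: "The latter would be accomplished following projection of the data into a Cartesian plane, e.g. via non-metric multidimensional scaling (NMDS"). For its other techniques the section points back to a list for microbiome profiling, but section 11 contains no microbiome part.

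Neither section gives a range for the number of clusters, a one-cluster option, a reference for data without clusters, a stability check, or wording for a negative result. The training, validation and testing split in 11.1 is written for predictive models, and the false discovery rate rule in 11.6 is written for P-values.

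**The concern.** Read together, the two sections write out a complete path: reduce to a plane, run k-means, pick the number of clusters by silhouette. Two features of that path are troublesome.

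First, the criterion compares each participant's distance to their own group with the distance to the nearest other group. With one group there is no comparison, so one group can never be chosen.

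Second, silhouette is higher in two dimensions than in many, even when there is nothing to find. An analyst who sees 0.4 on a plot may read it as moderate structure.

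The trial describes itself as discovery-based and looks for biomolecular signatures and their associations with clinical outcomes. Spurious groups, if reported, would be hard to expose afterwards with about 92 evaluable participants.

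**Working it through.** The documents give no figure for clustering, so there is none to reproduce. The check is the definition of the criterion followed by simulation.

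**Inputs.** n = 92 is the final sample in sections 11.2 and 11.5. The number of markers, their correlation and the range of k are not stated. The assumptions were 12, 24 or 200 Gaussian markers, either independent or driven by two continuous factors, with k from 2 up to 6 or 8. No simulated data set contained clusters.

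**Step 1, the criterion.** For participant i, s(i) = (b − a) / max(a, b), where a is the mean distance to the rest of the participant's own cluster and b is the mean distance to the nearest other cluster. At k = 1, b does not exist. The smallest k that can be selected is therefore 2. In the simulations with 12 and 200 markers, at least two clusters were returned in 100% of runs for every input.

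**Step 2, the size of the silhouette without clusters.** Mean best value, k-means. The first two columns are independent markers (40 and 30 runs):

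| Input to k-means | 12 markers | 200 markers | 24 two-factor markers |
|---|---|---|---|
| Markers themselves | 0.089 | 0.008 | 0.07–0.14 |
| First two PCA scores | 0.38 | 0.38 | 0.37–0.39 |
| t-SNE, perplexity 5 | 0.43 | 0.39 | – |
| t-SNE, perplexity 20 | – | – | 0.40 |
| t-SNE, perplexity 30 | 0.38 | 0.35 | – |
| NMDS, two dimensions | 0.35 | 0.35 | – |

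The last column spans several runs at different assumed factor strengths. A plain two-dimensional Gaussian cloud, with no reduction at all, gave 0.37 to 0.38. With 12 and 200 markers, every two-dimensional run exceeded 0.25, no raw-marker run did, and no run exceeded 0.5. U-MAP was not simulated.

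**Step 3, criteria already listed in 11.1 that can return one cluster.** These were Gaussian mixtures with k = 1 to 5 on the two-dimensional coordinates, for 12 and 200 independent markers.

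- BIC chose k = 1 in 100% of runs on PCA, NMDS and t-SNE at perplexity 30. On t-SNE at perplexity 5 it did so in 88% (12 markers) and 100% (200 markers).
- AIC chose k = 1 in 78–80% on PCA, 0–77% on t-SNE at perplexity 5, 98–100% on t-SNE at perplexity 30, and 100% on NMDS.

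**Step 4, which reference to use.** One option is to permute each marker column independently and repeat the pipeline.

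- With 12 independent markers reduced to two PCA scores, 19 permutations (nominal 1/20 = 5%) gave a false declaration in 4 of 40 runs, or 10%, which is compatible with 5% at that number of runs.
- With 24 correlated two-factor markers clustered without reduction, the same device at a nominal 10% declared clusters in 15 of 15 cluster-free data sets. Permuting columns destroys the correlation, so the test rejects because markers are correlated, not because clusters exist.
- A multivariate normal reference with the observed covariance declared clusters in 0 of 15.

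Real biomarkers in one disease pathway will be correlated, so the second situation is the relevant one.

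**The case against.** The strongest reply is that section 11.1 is a menu, not a commitment. Reduction is optional there, PCA is named first in both sections, k-means in 11.6 is something the plan may include, and silhouette is one of three example criteria. BIC with Gaussian mixtures is already on the list and mostly gave the right answer in step 3. All of this stands. It means the plan contains a sound route; it does not mean the plan requires it. The k-means route is the one 11.6 spells out, and AIC, also allowed, is less reliable.

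Three stronger readings are tempting and are not supported.

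- **That the plan will report patient subtypes.** No aim names clustering or subtypes. Aims 1 and 2 use generalized additive and multilevel models, and section 11.6 relates clinical to molecular data by correlation and regression. It does not even say whether participants, samples or genes are clustered.
- **That t-SNE manufactures the groups.** Two PCA scores and a plain two-dimensional cloud give nearly the same silhouette. The rise comes from reduction to two dimensions, so barring particular embeddings would not cure it.
- **That unstable assignments between t-SNE runs prove distortion.** Pairs of t-SNE runs agreed poorly (mean adjusted Rand index 0.12 to 0.50, depending on assumed structure), but the start and perplexity were changed together. With no true clusters, any partition is arbitrary.

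**Conclusion.** The concern holds in a limited form. The plan permits k-means on low-dimensional coordinates with silhouette choosing the number of clusters. That path cannot return one cluster, and no check that clusters exist is stated, so spurious groups could be reported.

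That silhouette cannot select one cluster follows from its definition and needs no assumption. The sizes rest on Gaussian markers, 92 participants and assumed marker numbers and correlations. The two-dimensional result (about 0.35 to 0.43) varied little across those assumptions; the raw-marker result (about 0.01 to 0.14) depended on them more. The good behaviour of BIC was shown on Gaussian data only, and skewed markers could lead a mixture to add components.

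Severity is minor. Clustering is exploratory, lies outside Aims 1 to 4, and does not touch the models for Aims 1 and 2.

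**What to change.** In sections 11.1 and 11.6:

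1. Reconcile the two statements on reduction, optional in 11.1 and a first step in 11.6. Replace the pointer to a microbiome list with the methods meant, and say what is clustered.
2. Choose the number of clusters with a criterion that allows one: BIC for Gaussian mixtures, already listed, or the gap statistic. If silhouette is kept, use it to describe a solution, not to decide that one exists.
3. Report clusters only if they exceed a single-population reference put through the same pipeline. The reference must keep the marker correlations, for example multivariate normal data with the observed covariance. Independently permuted columns do not serve.
4. Require stability on bootstrap resampling, with the threshold set by the study biostatistician before the data are seen. The documents give no basis for a particular value.
5. State that otherwise the report will say no clusters were found.

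The cost is a few sentences and a modest amount of computing in R, with no new data. The downside is slightly more analysis work and fewer reported clusters.
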